9.7 Efficacy Subgroup Analyses

Subgroup analysis for the primary endpoint will be conducted by the subgroups specified below. The difference in the primary efficacy endpoint between the treatment groups in each subgroup will be assessed using CMH approach. Treatment difference and corresponding confidence interval will be used to summarize the result.

- Number of prior failed b/tsDMARDs (1; 2 or more)
- Prior anti-TNF failure (yes/no)
- Prior use of adalimumab (yes/no)
- Age (< median; ≥ median years)
- Sex (female; male)
- Race (white; non-white)
- Geographic region (North America, Asia, Rest of World)
- BMI (< 25, ≥ 25 - < 30, ≥ 30 kg/m²)
- Baseline glucocorticoid use (yes/no)

If any subgroup has fewer than 10% of the total subjects, then the analysis for this subgroup will not be performed.

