7.4 Statistical Analyses for Efficacy

For the Placebo-Controlled Period, subjects will be analyzed according to the treatment group randomized. All statistical tests will be performed at a 2-sided significance level of 0.1. A 95% confidence interval of the treatment difference between each ABBV-154 dose and placebo will be provided.

- For categorical variables, a pairwise, comparison will be made between each ABBV-154 dose and placebo using the Cochran-Mantel-Haenszel (CMH) test, adjusting for the actual values of stratification factors. Non-Responder Imputation incorporating multiple imputation to handle COVID-19 (NRI-MI) will be the primary approach to handle missing data for categorical endpoints.
- For continuous variables, the comparison will be made between each ABBV-154 dose and placebo based on the MMRM adjusting for treatment, visit, interaction between treatment and visit, actual values of stratification factors as fixed factors, and BL value as a covariate. The MMRM will be the primary approach to handle missing values for continuous endpoints.

Through the Placebo-Controlled and Long-Term Extension Periods, descriptive statistics by treatment sequences will be provided at each visit. Categorical endpoints will be summarized by the number and proportion of subjects who achieved the endpoint, as well as the 95% confidence interval. Continuous endpoints will be summarized by descriptive statistics including mean, standard deviation, standard error, and the 95% confidence interval of the mean. In addition, continuous endpoints through Week 24 will be summarized using estimates from the MMRM by treatment sequence, visit, interaction between treatment sequence and visit, actual values of stratification as fixed factors and baseline values as a covariate.

Summary and Analysis of the Primary Endpoint

The primary endpoint is the achievement of ACR50 at Week 12. It will be evaluated using the ITT Population based on treatment as randomized. Comparison of the primary endpoint will be made between each ABBV-154 dose and placebo using the CMH test adjusting for the actual values of stratification factors. NRI-MI will be the primary approach to handle missing values. Analysis details for NRI-MI and other sensitivity analyses (if applicable) will be provided in the SAP.

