One supplementary analysis for primary endpoints is to test a pre-specified set of dose-response models among ABBV-154 dose groups and the placebo group at Week 12 using the Multiple Comparison Procedure – Modeling approach (MCP-Mod). Details of this method will be provided in the SAP.

Summary and Analysis of Secondary Endpoints

Analysis of secondary efficacy endpoints will be conducted on the ITT Population based on treatment as randomized.

Summary and Analysis of Additional Efficacy Endpoints

Additional endpoints, as described in Section 3.3, will also be analyzed.

Subgroup Analysis for Efficacy

To evaluate the consistency of efficacy across demographic and other Baseline characteristics, the following subgroup analysis will be performed on the primary endpoint:

- Baseline glucocorticoid use (yes/no)
- Number of prior failed b/tsDMARDs (1; 2 or more)
- Prior use of failed anti-TNF (yes/no)
- Prior use of adalimumab (yes/no)
- Age (\leq median/ $>$ median)
- Sex (female/male)
- Race (white/non-white)

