2.4 Sample Size Determination

The planned total sample size of 425 subjects (approximately 85 subjects per treatment group) provides at least 90% power to detect a 22% difference between ABBV-154 and placebo in ACR50 response rate at Week 12 (assuming a placebo ACR50 response rate of 13%), at a 2-sided significance level of 0.1 based on Chi-square test.

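### SAP 9.7 gives a treatment difference and interval within each subgroup but no estimate of the difference between subgroups, which is what the protocol's consistency aim is about

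*SAP*

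**What the plan says.** Protocol 7.4, under its subgroup heading, gives the purpose as "To evaluate the consistency of efficacy across demographic and other Baseline characteristics", applied to ACR50 at Week 12.

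SAP 9.7 gives the method: "The difference in the primary efficacy endpoint between the treatment groups in each subgroup will be assessed using CMH approach". The output is described in one sentence: "Treatment difference and corresponding confidence interval will be used to summarize the result". Nine factors are listed. Seven have two levels; geographic region and BMI have three. A subgroup holding fewer than 10% of subjects is not analysed. With four active regimens against placebo there are 9 × 4 = 36 factor-by-dose displays.

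SAP 9.7 does not state the interval level. Protocol 7.4 says generally that "A 95% confidence interval of the treatment difference between each ABBV-154 dose and placebo will be provided", while "All statistical tests will be performed at a 2-sided significance level of 0.1". Neither document plans a treatment-by-subgroup term, a homogeneity test, or an interval for the difference between subgroup effects. SAP section 13.0 plans no multiplicity control.

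**The concern.** Consistency is a statement about a contrast: how different the treatment effect is in one level from the effect in the other. The plan estimates the two effects separately and stops there, so the quantity named as the aim is never produced.

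With no contrast and no stated rule, a reader may fall back on asking which intervals exclude zero. That depends heavily on subgroup size, and it can suggest that the drug works in one group and not in another when the effect is the same in both. The question matters here because ABBV-154 is built on adalimumab, prior anti-TNF failure and prior adalimumab use are stratification factors, and enrolment of adalimumab-experienced subjects is capped. That smaller group is the one most exposed to such a misreading.

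**Working it through.** **Inputs from the documents.** SAP 2.4: "approximately 85 subjects per treatment group", placebo ACR50 rate 13%, difference 22 points, hence 35% on active drug. Interval level 95% (Protocol 7.4). Two splits follow from the documents: age at the median, about 50:50 (42 and 43 per arm), and prior adalimumab use capped at about 30%, so 30:70 if the cap is reached (0.30 × 85 = 25.5, taken as 26 and 59 per arm).

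**Assumptions of this check.** The same effect in both levels; unstratified Wald intervals, because the SAP does not name an interval method; discordant means that exactly one of the two intervals excludes zero.

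**Step 1, the plan's own figure.** SAP 2.4 says the sample size "provides at least 90% power to detect a 22% difference between ABBV-154 and placebo in ACR50 response rate at Week 12". The pooled rate is 0.24.
- Null SE = √(2 × 0.24 × 0.76 / 85) = 0.0655
- Alternative SE = √((0.13 × 0.87 + 0.35 × 0.65) / 85) = √(0.3406 / 85) = 0.0633
- Power at two-sided 0.1 = Φ((0.22 − 1.645 × 0.0655) / 0.0633) = Φ(1.77) = 96%

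The stated figure holds.

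**Step 2, chance that each level's 95% interval excludes zero.** This is the sum of the binomial probabilities over all outcome pairs whose Wald interval excludes zero.
- 50:50: 0.689 (n = 42) and 0.702 (n = 43)
- 30:70: 0.488 (n = 26) and 0.823 (n = 59)

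**Step 3, discordance.** The levels contain different subjects, so P = P1(1 − P2) + P2(1 − P1).
- 50:50: 0.689 × 0.298 + 0.702 × 0.311 = 0.42
- 30:70: 0.488 × 0.177 + 0.823 × 0.512 = 0.51

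With 90% intervals the level probabilities are 0.788 and 0.798 (50:50), and 0.603 and 0.897 (30:70). Discordance is then 33% and 42%.

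**Step 4, sensitivity to the uniform effect** (placebo 13%, 95% intervals, same formulas):

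| Active rate | 50:50: P1, P2 | Discordant | 30:70: P1, P2 | Discordant |
|---|---|---|---|---|
| 20% | 0.143, 0.146 | 25% | 0.111, 0.189 | 26% |
| 25% | 0.298, 0.306 | 42% | 0.208, 0.400 | 44% |
| 30% | 0.495, 0.508 | 50% | 0.340, 0.636 | 54% |
| 35% (design) | 0.689, 0.702 | 42% | 0.488, 0.823 | 51% |
| 40% | 0.837, 0.847 | 27% | 0.635, 0.932 | 38% |
| 45% | 0.927, 0.934 | 13% | 0.763, 0.980 | 25% |

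**Step 5, the contrast the plan omits.** For a level holding share s, SE of the between-level difference = 0.0633 × √(1/s + 1/(1 − s)).
- s = 0.5: 0.0633 × 2 = 0.127; 95% half-width 1.96 × 0.127 = 25 points
- s = 0.3: 0.0633 × 2.182 = 0.138; 95% half-width 27 points

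Under a uniform effect this interval excludes zero about 5% of the time, by construction.

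**Step 6, reading by overlap instead.** The two 95% intervals fail to overlap only if the estimates differ by more than 1.96 × (SE1 + SE2).
- 50:50: 1.96 × (0.0895 + 0.0895) = 0.351, which is 0.351 / 0.127 = 2.77 SEs of the contrast: probability 0.6%
- 30:70: 0.227 + 0.148 = 0.375, which is 0.375 / 0.138 = 2.71 SEs: probability 0.7%

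**The case against.** The strongest reply is that the plan contains no pass/fail rule. SAP 9.7 says only that differences and intervals will summarise the result. Read as estimates with uncertainty, they serve well enough: under a uniform design effect the two intervals almost always overlap, and simulation puts the estimates on opposite sides of zero in only about 1% (50:50) to 2% (30:70) of comparisons. This stands, and it is why the 42% and 51% must be stated as conditional.

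Second, 22 points at every dose is not what a dose-ranging plan expects. Under the Emax candidate in SAP 9.6 (ED50 83.9), if 340 mg EOW gives 22 points then 40 mg gives 22 × (40/123.9) / (340/423.9) = 9 points, an active rate near 22%. That falls between the 20% and 25% rows above. This also stands.

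Third, the contrast and its approximate interval can be worked out by hand from the two reported differences, and each reported interval already shows its own imprecision. That is true, but the reader should not have to derive the one quantity that matches the stated aim.

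Three stronger readings are tempting and unsupported. A reader might infer that the plan itself will make a uniform effect look inconsistent about half the time; that needs the excludes-zero rule, which the documents do not contain. A reader might count expected discordances over all 36 displays; the documents give neither the subgroup shares nor a common effect across doses. A reader might infer that subgroup results will decide the Phase 3 population; Protocol 7.1 says only that additional analyses may inform the Phase 3 design and does not mention subgroups.

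**Conclusion.** The gap is real and rests on the text alone: the aim is consistency, and no estimate compares subgroup levels. Its practical size depends on how the tables are read. If judged by which 95% intervals exclude zero, a uniform 13% versus 35% effect would look discordant in about 42% (50:50) or 51% (30:70) of two-level comparisons. The 30:70 figure assumes that the adalimumab cap is reached, and both rest on unstratified Wald intervals. Over active rates from 20% to 45% the figure runs from 13% to 54% at these two splits. If judged by overlap, it is under 1%.

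The weight is modest. This is a Phase 2b study with openly unadjusted comparisons, and neither the primary analysis nor its power is affected.

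**What to change.** In SAP 9.7, for each factor and each dose versus placebo, add the difference between the subgroup-level treatment differences with its 95% confidence interval. For region and BMI, use contrasts between levels or a treatment-by-subgroup term. State the interval level in that section. State also that consistency is judged descriptively on this contrast, and not on whether each subgroup interval excludes zero.

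The cost is a sentence or two in the SAP and one extra table column, computed from estimates already planned. The downside is imprecision. With half-widths of 25 to 27 points, wider than the 22-point target, the contrast cannot serve as a test. At 50:50 its power for a true 22-point difference between levels is Φ(0.22 / 0.127 − 1.96) = 41% at two-sided 0.05. It should be presented as an estimate only, which also shows plainly how little the trial can say about heterogeneity.

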10.0 Safety Analyses

10.1 General Considerations

Safety data will be summarized for each safety population (Safety_PC and ALL_154). Safety summaries will be presented by treatment group, including a total group for all subjects on active study drug. For the safety analysis, subjects are assigned to a treatment group based on the treatment actually received, regardless of the treatment randomized.

"Baseline" refers to the last non-missing observation before or on the day of the first administration of study drug or randomization if no study drug is given. Observations on the same day as the first administration of study drug will be considered for baseline,

regardless if observation time (if available) was after the first administration of study drug time.

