10.2.1 Treatment-Emergent Adverse Events

Treatment-emergent AEs are defined as any AE with the onset that is after the first dose of study drug and with an onset date no more than 5 half-lives of the study drug (i.e., 70 days). Events where the onset date is the same as the study drug start date are assumed to be treatment-emergent, unless the study drug start time and the AE start time are collected and the AE start time is prior to the study drug start time. All treatment-emergent AEs will be summarized overall, as well as by primary MedDRA SOC and Preferred Term. The SOCs will be presented in alphabetical order, and the PTs will be presented in alphabetical order within each SOC.

The number and percentage of subjects experiencing treatment-emergent AEs will be summarized.

In the ALL_154 population, treatment-emergent AEs are defined based on the first dose of ABBV-154.

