10.3 Analysis of Laboratory Data

Data collected from central and local laboratories, including additional laboratory testing due to an SAE, will be used in all analyses, except for Baseline where SAE-related laboratory assessments on or before the first dose of study drug will be excluded. The clinical laboratory tests defined in the protocol operations manual (e.g., hematology and clinical chemistry) will be summarized.

Each laboratory variable will be summarized for all time points (starting with Baseline) with the number of non-missing observations, mean and standard deviation, median, minimum and maximum. Mean change from baseline to each applicable post-baseline visit will be summarized for selected laboratory variables, with the number of observations, baseline mean, and visit mean. The change from baseline mean, standard error, and 95% confidence interval will be presented for the mean change from baseline within each treatment group and difference between treatment groups (ABBV-154 vs. placebo) as applicable. This summary and change from baseline summary will be presented once by treatment sequence.

Changes in laboratory parameters will be tabulated using shift tables either by NCI CTC criteria or other criteria listed in Appendix B. A shift table from baseline either to the worse value (based on NCI CTC criteria) during treatment or to minimum and maximum value (based on normal range), will be created. A similar shift table will be provided to summarize shifts from baseline to the final post-baseline value.

Laboratory abnormalities meeting CTC criteria grade 3 and 4 will be summarized.

Laboratory abnormalities will be evaluated based on Potentially Clinically Important (PCI) criteria (based on NCI CTC criteria, except for those listed in Appendix B). For each laboratory PCI criterion, the number and percentage of subjects who have a laboratory value meeting the criteria will be summarized. Listings will be provided to summarize subject-level laboratory data for subjects meeting PCI criteria. In the evaluation of PCI laboratory values, the baseline value for the ALL_154 population will

be determined by the last non-missing measurement recorded on or before the date of the first dose of study drug in the corresponding ABBV-154 treatment group (which may be different than the first dose of study drug received in the study).

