For the purpose of assessing for potential Hy's law cases, the frequencies and percentages of subjects with post baseline liver specific function test values that meet the following criteria of potential clinical interest will be summarized by "as treated" treatment group:

- $ALT > 3 \times ULN$
- $ALT > 5 \times ULN$
- $ALT > 10 \times ULN$
- $ALT > 20 \times ULN$
- $AST > 3 \times ULN$
- $AST > 5 \times ULN$
- $AST > 10 \times ULN$
- $AST > 20 \times ULN$
- $TBL > 2 \times ULN$
- Alkaline phosphatase $> 1.5 \times ULN$
- ALT and/or $AST > 3 \times ULN$ and concurrent $INR > 1.5$
- ALT and/or $AST > 3 \times ULN$ and concurrent $TBL > 2 \times ULN$

A listing of possible Hy's Law cases, defined as those who meet all of the following conditions simultaneously, will be provided: $ALT > 3 \times ULN$ or $AST > 3 \times ULN$ that is associated with an increase in bilirubin $> 2 \times ULN$.

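### For placebo subjects who switch at Week 12, the SAP's default baseline leaves the ALL_154 laboratory shift tables anchored at Day 1 and does not keep placebo-period values out of the liver-test and grade 3/4 counts

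*SAP*

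**What the plan says.** Protocol 5.7 uses the term study drug for ABBV-154 and for placebo. Under SAP 2.3, placebo subjects are re-randomized 1:1 at Week 12 to ABBV-154 150 mg or 340 mg eow. Under SAP 4.0 they belong to ALL_154 once they have had one ABBV-154 dose.

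SAP 10.1 announces safety summaries for Safety_PC and ALL_154 and gives a single baseline definition, which "refers to the last non-missing observation before or on the day of the first administration of study drug". The SAP then writes three exceptions for ALL_154:

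- SAP 10.2.1, adverse events: "In the ALL_154 population, treatment-emergent AEs are defined based on the first dose of ABBV-154".
- SAP 10.3, PCI laboratory values: a sentence that opens "In the evaluation of PCI laboratory values, the baseline value for the ALL_154 population will" goes on to take the last value up to the first dose in the subject's ABBV-154 group. It adds in parentheses that this dose need not be the first study-drug dose in the study.
- SAP 10.4, PCI vital signs: the same rule.

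Three other laboratory outputs have no such exception:

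- Shift tables: "A shift table from baseline either to the worse value (based on NCI CTC criteria) during treatment", or to the minimum and maximum, plus a similar table to the final post-baseline value.
- The summary of grade 3 and 4 abnormalities, which mentions neither a baseline nor a window.
- The Hy's law paragraph, which counts "subjects with post baseline liver specific function test values that meet the following criteria", by as-treated group.

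**The concern.** A subject who takes placebo until Week 12 and ABBV-154 afterwards has two candidate baselines. The SAP's authors recognised this where they wrote the PCI rule, but the correction stops at PCI values and TEAEs. Elsewhere the general definition applies, and it leads to the first placebo dose.

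Two things are at stake. The first is consistency: HbA1c, HDL and LDL use the Appendix B categories in both the shift tables and the PCI evaluation, so the same switcher could have one baseline category in one table and another in the next. The second is attribution: a liver-test elevation during the placebo weeks is post baseline by the Day 1 definition, and an ALL_154 table could then show it under ABBV-154 150 mg or 340 mg eow. The 40 mg eow and 340 mg e4w groups receive no switchers, so any such error falls on two of the four regimens only.

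**Working it through.** **1. The plan's own figure.** SAP 2.4 states: "The planned total sample size of 425 subjects (approximately 85 subjects per treatment group". With 1:1:1:1:1 allocation, 425 / 5 = 85, which agrees. The accompanying claim that this "provides at least 90% power to detect a 22% difference between ABBV-154 and placebo" also reproduces. With 13% against 35%, n = 85 per group and two-sided alpha 0.1:

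- null SE = sqrt(2 x 0.24 x 0.76 / 85) = 0.0655
- alternative SE = sqrt((0.13 x 0.87 + 0.35 x 0.65) / 85) = 0.0633
- z = (0.22 - 1.645 x 0.0655) / 0.0633 = 1.77, so power is 96.2%

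The 85 is therefore a sound planning number. Here it serves only as the size of the placebo arm.

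**2. Where the anchor falls for a switcher in ALL_154, read literally.**

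| ALL_154 output | Anchor for a switcher | Uses a baseline value? | Can placebo-period values enter? |
|---|---|---|---|
| TEAEs (10.2.1) | first ABBV-154 dose | no | no |
| PCI laboratory values and vital signs (10.3, 10.4) | first ABBV-154 dose, for the baseline value | yes | post-baseline window not stated separately |
| Shift to worst, minimum or maximum (10.3) | Day 1 by default (10.1) | yes | yes, if the window also starts at Day 1 |
| Shift to final value (10.3) | Day 1 by default (10.1) | yes | only through the starting value |
| Grade 3/4 summary (10.3) | not stated | none mentioned | not excluded |
| Liver-test counts (10.3) | post baseline, so Day 1 by default | no, fixed limits | yes, by the default |

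Protocol Appendix E schedules chemistry at Weeks 2, 4, 8 and 12. A switcher therefore has four scheduled samples after Day 1 and up to the first ABBV-154 dose. Haematology, HbA1c and lipids are also scheduled at Week 12, so a value from just before ABBV-154 is available.

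**3. Subjects concerned.**

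- Switchers: at most 85, because only those who reach Week 12 and are dosed with ABBV-154 count.
- Share of ALL_154: 85 / 425 = 20%.
- Each receiving group: 85 / 2 = 42.5 switchers added to 85 original subjects; 42.5 / 127.5 = 33%.

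**4. Illustration for the liver counts.** The documents give no 12-week placebo incidence, so it is an assumption, with a range of 1% to 5%.

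| Assumed incidence | Cases (85 x p) | Points of 425 | Cases per eow group (42.5 x p) | Points of 127.5 |
|---|---|---|---|---|
| 1% | 0.85 | 0.2 | 0.43 | 0.3 |
| 2% | 1.7 | 0.4 | 0.85 | 0.7 |
| 5% | 4.25 | 1.0 | 2.13 | 1.7 |

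These are upper limits on the excess. A subject who also crosses the threshold on ABBV-154 would be counted anyway.

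**The case against.** The best reply is that nothing in the SAP says placebo-period values are to be tabulated under ABBV-154, and that several phrases point the other way. Safety groups follow treatment actually received, the liver counts are by as-treated group, and the worst-value shift is to a value during treatment. SAP 4.0 assigns groups by majority exposure within an analysis period. If that period included placebo time, a switcher who stopped soon after Week 12 would fall into a placebo group in a population defined by ABBV-154, which suggests that the intended period starts at the first ABBV-154 dose. Shift and PCI tables also draw on the same criteria (NCI CTC or Appendix B), so the PCI sentence might be meant to cover both. The Product Safety SAP, which is not available here, might hold a convention too.

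This is fair evidence of intent, but it does not supply a rule. As-treated grouping decides the column a subject appears in, not the date from which values count. Being on placebo is also being on treatment. The analysis period for ALL_154 is not defined. The re-anchoring sentence is limited by its own words to PCI values, and its parenthesis shows that the two first doses were known to differ.

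Part of the reply does stand. The liver criteria are fixed multiples of ULN or a fixed INR limit, and the grade 3/4 sentence refers to no baseline. For these only the window is in question, not a conflicting baseline value.

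**Conclusion.** The gap is real and modest. For up to 85 switchers, SAP 10.1 followed literally puts the ALL_154 shift tables on a Day 1 baseline that disagrees with the PCI tables. It also lets placebo-period values into the liver-test counts, while the grade 3/4 summaries have no stated window. The possible size is about 1-4 liver cases over the two eow groups, on the assumed 1-5% incidence and with every placebo subject switching.

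A reader might infer more than this:

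- **That the SAP attributes the placebo period to ABBV-154.** It does not say so; that result follows only from the default definition.
- **That the trial's safety comparison between doses is distorted.** ALL_154 is a descriptive summary. The randomized comparison is in Safety_PC, where Day 1 is the right anchor. The laboratory summary and mean-change tables are by treatment sequence and so keep switchers separate, and TEAEs are already re-anchored.
- **That glucocorticoid tapering lowers HbA1c on placebo and so hides a later rise.** Nothing in the documents shows such a fall. HbA1c is also a PCI parameter with a re-anchored baseline.

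**What to change.** In SAP 10.1, state that for every ALL_154 summary the baseline is the last non-missing value on or before the first ABBV-154 dose, and that ALL_154 shift tables, grade 3/4 summaries and liver-test counts use only values after that dose. Keep the Day 1 baseline for Safety_PC and for the by-treatment-sequence summaries, and say so in the same place.

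The cost is a few lines of SAP text. The re-anchored laboratory baseline must already be derived for the PCI tables, and no new data are needed.

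The exposure definition in SAP 10.2.4 should be checked in the same edit, because it runs from the first dose date with no ALL_154 rule. For a switcher dosed through Week 180 it gives 180 x 7 + 70 = 1,330 days, of which 84 (6.3%) are placebo time.
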